#### 4.2. Baseline Questionnaire and Intermittent Fasting Education

After providing informed consent, participants will complete an online questionnaire. The baseline surveys will ask about dietary patterns and experiences with weight loss and dieting. Patients will also complete the Grit Scale and the MOS Social Support survey to obtain a psychometric profile relevant for persistence with a dietary intervention. They will also complete the 2005 Healthy Eating Index scale to assess pre-intervention diet quality.

Following completion of the baseline questionnaire, participants will receive education about intermittent fasting, including its definition, potential health benefits, and expectations about the experience.

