# 4. Study Procedures

#### 4.1. Screening and Informed Consent

Patients with body mass index  $> 30 \text{ kg/m}^2$  and SBP > 140 mmHg will be identified in select cardiology clinics and invited to participate. Interested participants will be instructed to visit the Way to Health platform online to register. They will also provide a contact number and email address, and will receive a reminder email and a phone call from a study coordinator for assistance with registration.

In addition, a data pull of potentially eligible participants will be performed during the study preparation phase. Once the research team obtains this eligibility list, the order of participants on the list will be randomized and then split into batches of 1000. The initial recruitment list will consist of 500 potentially eligible participants, which will help to ensure all the enrollment mechanisms are in place and working well. Three weeks after the initial recruitment emails/letters are sent, a second batch will be sent. Every 2-3 weeks thereafter, a new batch will be sent out until the randomization target is met. Interested participants will be provided with instructions to visit the Way to Health online platform to register for the study.

On the Way to Health platform, participants will learn more about the study, create an account, provide informed consent, and complete baseline study surveys. Study coordinators will be available to assist patients with this process, as necessary.

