We will follow an IRB-approved approach taken by many studies using the Way to Health platform to obtaining informed consent. Upon reaching the portal, potential participants will be asked to create an account and will then be informed of the details of the study, including its objectives, duration, requirements, and financial payments. The Way to Health portal will then take interested participants through an online informed consent. The consent document will be divided into sections and potential participants will have to click a button to advance through each section. This is to help ensure that participants read the consent form thoroughly by breaking down the form into manageable blocks of text. Each section will have a button allowing the user to contact a researcher via email or by telephone if they have questions about the consent form. Successive screens will explain the voluntary nature of the study, the risks and benefits of participation, alternatives to participation, and that participants can withdraw from the study at any time. On the final consent screen, potential participants who click a clearly delineated button stating that they agree to participate in the study will be considered to have consented to enroll. Participants will be provided with details regarding how to contact the research team via email or phone at any time if they subsequently wish to withdraw from the study. This contact information will remain easily accessible via the participants' individual Way to Health web portal dashboards throughout the study.

Support partners will provide verbal informed consent via telephone for their name, email address, and phone number to be stored in the study database.

Once participants have completed the informed consent process, they will be mailed a scale and blood pressure cuff.

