#### 4.3. Randomization

Once patients have received their scale and blood pressure cuff, they will be prompted by automated text message from the Way to Health platform to obtain a baseline weight and blood pressure. Once they provide baseline measurements and baseline questionnaires have been completed, they will be randomly assigned via the Way to Health platform to attention control or the soft commitment device using 1:1 allocation. Randomization will be stratified based on BMI ( $\leq$  and > 40 kg/m^2) and systolic blood pressure ( $\leq$  and > 160 mmHg) and will use blocks of 6 to ensure equal allocation over time.

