#### 4.4. Study Arms

#### 4.4.1 Attention control

These patients will be instructed via text message and email to fast at least 16 hours per day every day. For the next 16 weeks, they will receive a daily text message via the Way to Health

platform asking if they fasted for at least 16 hours over the past 24 hours. If they fail to respond, reminder text messages will be sent. Once per week, they will receive a text message asking them to weigh themselves and check their blood pressure, and reply with the results via text message

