#### 5. Statistical Methods

# 5.1 Primary and secondary outcome measures

The study's primary outcome measure is adherence to the IF regimen, captured via daily text message, over 18 weeks, expressed in days per week.

Secondary outcome measures will include:

- 1) Adherence to the IF regimen over 12 weeks
- 2) Change in systolic blood pressure from baseline to 12 weeks and 18 weeks
- 3) Change in weight from baseline to 12 weeks and 18 weeks

Exploratory analyses will compare change in blood pressure and weight in patients that were adherent to IF  $\geq$  4 days per week vs.  $\leq$  4 days per week

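### Fasting education normally precedes the baseline weight and blood pressure, so within-arm change and the exploratory adherence comparison may be attenuated; the randomised comparison is not biased

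*Combined protocol and SAP*

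**What the plan says.** The order of events has to be assembled from several sections of the combined protocol and SAP.

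- Section 4.1: on the platform, "participants will learn more about the study, create an account, provide informed consent, and complete baseline study surveys". Then: "Once participants have completed the informed consent process, they will be mailed a scale and blood pressure cuff".
- Section 4.2: "Following completion of the baseline questionnaire, participants will receive education about intermittent fasting, including its definition, potential health benefits, and expectations about the experience".
- Section 4.3: "Once patients have received their scale and blood pressure cuff, they will be prompted by automated text message" to take the baseline weight and blood pressure. After that: "Once they provide baseline measurements and baseline questionnaires have been completed, they will be randomly assigned via the Way to Health platform".
- Section 4.4, attention control: "These patients will be instructed via text message and email to fast at least 16 hours per day every day". The commitment-device arm's fasting times and pledge are likewise set up only after assignment.

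Section 5.1 uses the baseline readings for two secondary outcomes: change in systolic blood pressure, and "Change in weight from baseline to 12 weeks and 18 weeks". Section 5.3 compares these changes between arms with mixed models. It also plans an exploratory comparison of the same changes by reported days fasted per week. The primary outcome, days fasted per week, uses no baseline value.

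**The concern.** A patient who completes the questionnaire promptly learns what intermittent fasting is, and what it may do for health, while the scale and cuff are still in the mail. The gap before the baseline reading is shipping time plus response time, and the protocol bounds neither. The daily fasting question is described only within the arms, so fasting begun in this gap would not be seen.

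Fasting begun before the reading can lower the recorded baseline and so shrink the measured change. Early starters are likely to be the later adherers, so the shrinkage would fall mainly on the adherent group in the exploratory comparison. That comparison matters because section 6.6.1 says both arms are told to fast. The randomised contrast therefore tests the commitment device, and what the trial can show about fasting itself comes from within-arm change and the comparison by adherence.

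Section 4.2 does place the diet-quality questionnaire before the education. Weight and blood pressure do not have the same protection.

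**Working it through.** **1. The plan's own figure.** The plan gives no number for this point. The nearest is the power of about 50% in section 5.2 for a 10 mmHg difference with SD 15 and 17 per arm. Assuming two-sided alpha 0.05 (not stated), the standard error is 15 × √(2/17) = 5.145. Then z = 10/5.145 − 1.960 = −0.016, giving power 0.493 (0.470 with the noncentral t). The figure is reproduced.

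**2. Loss for one early starter.** Inputs: 3 kg (sections 1.2 and 5.2) and 5–10 mmHg (section 1.2). Assumptions: the effect builds linearly, is complete after 12 weeks of fasting, and the gap is 1–4 weeks. Loss = gap/12 × effect.

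- Weight: 1/12 × 3 = 0.25 kg; 4/12 × 3 = 1.0 kg.
- Systolic pressure: 1/12 × 5 = 0.4 mmHg; 4/12 × 10 = 3.3 mmHg.

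The levelling-off matters. If the effect kept building at the same rate, the measured change would be (12 + gap)/12 − gap/12 = 1 times the effect, with no loss. If blood pressure responds faster than weight, its loss is larger.

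**3. Within-arm average.** Average loss = share starting early × loss per starter. The share is not documented. At an assumed 25%, it is 0.25 × 0.25 = 0.06 kg to 0.25 × 1.0 = 0.25 kg, or 0.25 × 0.4 = 0.1 to 0.25 × 3.3 = 0.8 mmHg. At 0% it is nil.

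**4. Between-arm contrast.** Education and baseline both precede assignment, so expected baseline is the same in both arms. The expected difference in change therefore equals the expected difference at follow-up, and early fasting cancels. What remains is noise. If half start early and each loses 3.3 mmHg, independently of everything else, the added variance is 0.5 × 0.5 × 3.3² = 2.7. The SD becomes √(225 + 2.7) = 15.09 instead of 15, and power moves from 0.493 to about 0.489.

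**5. Simulation of direction.** Each scenario has 2,000,000 patients. All of the following are assumptions: a full fasting effect of −7.5 mmHg (midpoint of 5–10), scaled by days fasted/7; mean adherence 4 (control) and 5 (device) days per week; the most motivated patients start early; and a stated share of the full effect is already present at baseline. The plan's exploratory groups overlap at exactly 4 days, so ≥4 versus <4 was used. Entries are mean systolic change or difference in mmHg.

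| Start early | Effect present at baseline | Control | Device | Device − control | ≥4 − <4 days |
|---|---|---|---|---|---|
| 0% | none | −4.28 | −5.35 | −1.07 | −2.15 |
| 25% | 25% | −3.81 | −4.87 | −1.06 | −1.45 |
| 25% | 50% | −3.35 | −4.39 | −1.04 | −0.76 |
| 25% | 100% | −2.41 | −3.47 | −1.06 | +0.65 |
| 50% | 25% | −3.34 | −4.40 | −1.05 | −1.03 |
| 50% | 50% | −2.41 | −3.46 | −1.05 | +0.11 |
| 50% | 100% | −0.53 | −1.59 | −1.06 | +2.31 |

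Across all runs the between-arm difference stayed between −1.04 and −1.10, which is simulation noise. Within-arm change shrinks in every early-start scenario. The exploratory contrast moves toward zero and reverses only under the heavier assumptions.

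**The case against.** A reader might infer that the secondary outcomes lose part of the treatment effect, or that 0.25–1.0 kg is the damage to the trial's result. The documents do not support either reading. Section 5.3 compares change between randomised arms, and steps 4 and 5 show that contrast unbiased. The primary outcome has no baseline to contaminate.

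Other objections, and what stands of each:

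- *The order is inferred.* This stands. Section 4.2 ties education to the questionnaire, devices are mailed in parallel, and section 4.3 does not order questionnaire and readings. A patient who finishes the questionnaire late could be measured first. The sequence is the normal one, not a fixed one.
- *No within-arm analysis is specified, and the adherence comparison is confounded by motivation anyway.* This stands, and it limits the importance of the point. Still, the adherence comparison is planned, and a baseline taken after education adds an avoidable distortion.
- *Early starting is undocumented.* This stands: gap, share and accrual are all assumed.
- *Consent pages are not among the documents.* This stands. The missing safeguard is a statement about the protocol text only; participant-facing instructions may contain one.
- *Education after assignment could be taken up differently by arm.* This is a fair objection to such a placement, since the device arm then has its own platform tasks. Placing the education before assignment meets it.

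**Conclusion.** The point holds in a limited form. As described, education normally comes before the baseline readings, the gap is unbounded, and the protocol text neither discourages nor records early fasting. If some patients start early and the effect levels off by the time of assessment, within-arm change is understated and the exploratory adherence comparison is biased, probably toward no difference.

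The documents do not allow the size to be estimated. The per-patient range in step 2 depends on the assumed gap and accrual, and the trial average could be close to zero. The randomised comparison and primary outcome are affected only by a little possible noise and chance imbalance. Severity: minor, an optional improvement. Confidence is good on the usual sequence and low on the magnitude.

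**What to change.** 1. In sections 4.2 and 4.3, deliver the education module after baseline weight and blood pressure are submitted and before the arm is assigned, and add its completion to the conditions for randomisation. Delivery then stays identical and blind to arm. The questionnaire stays where it is.
2. Add one sentence at consent asking participants to keep their usual eating pattern until they receive the start message.
3. Add one baseline item asking whether fasting has already begun, so that the exploratory analysis can describe early starters or be repeated without them.

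The cost is a reordered automated module, one sentence and one question, with no extra patients, visits or staff. The downside is one more platform step between baseline and randomisation. Consent already discloses the study's objectives, so early starting would be reduced rather than eliminated.

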#### 4.3. Randomization

Once patients have received their scale and blood pressure cuff, they will be prompted by automated text message from the Way to Health platform to obtain a baseline weight and blood pressure. Once they provide baseline measurements and baseline questionnaires have been completed, they will be randomly assigned via the Way to Health platform to attention control or the soft commitment device using 1:1 allocation. Randomization will be stratified based on BMI ( $\leq$  and > 40 kg/m^2) and systolic blood pressure ( $\leq$  and > 160 mmHg) and will use blocks of 6 to ensure equal allocation over time.

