# 3. Study Design

#### 3.1. General Overview

The IFAST study is a two-arm randomized controlled trial aimed at evaluating whether a soft commitment device increases uptake and adherence to an intermittent fasting dietary pattern compared with control in patients with hypertension and obesity. The study will randomize 34 patients with hypertension and obesity to a 12-week intervention employing a commitment pledge, involvement of a supportive partner, setting of implementation intentions, and multiple daily reminder text messages or to an attention control involving daily text messages alone.

Following the intervention, there will be a 6-week follow-up period (see study protocol figure below).

The study will be conducted using Way to Health, a research information technology platform at the University of Pennsylvania used previously for behavioral interventions.

After institutional review board (IRB) approval of the study, patients who meet the eligibility criteria will be approached in select cardiology clinics and invited to participate. Those who qualify and express interest will provide informed consent to the study procedures via the Way to Health platform. All patients will receive a blood pressure cuff and scale, which will be used to measure blood pressure and weight weekly. Within the Way to Health platform, patients will be randomized to the intervention or control arms. All other management decisions are completely at the discretion of the care providers. Data capture will include:

- **Baseline case report form** (for each patient) collecting clinical information abstracted from the medical record
- **Baseline survey** collected via the Way to Health platform including psychometric questions, dietary patterns, and experiences with weight loss and dieting
- Daily adherence to an intermittent fasting dietary pattern collected via self-report from text messages
- Weekly weight and blood pressure measurement collected via self-report from text messages

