#### 4.4.1. Soft commitment device

Patients randomized to the commitment device arm will be asked to visit the Way to Health platform. There, they will identify a support person, a family or friend who they speak to frequently and who is invested in their health. They will then complete a series of questions intended to create implementation intentions. Specifically, they will pick a time for their fast to begin each 24-hour period and a time for their fast to end. They will also develop strategies to deal with hunger arising during a fast period. After this process, they will sign a contract pledging to adhere to the 16:8 time-restricted feeding dietary pattern, and acknowledging that their support person will receive a copy of the contract and weekly updates about their adherence to the regimen.

For the next 12 weeks, participants in this arm will receive reminder text messages two times daily via Way to Health: Once at the start of their fast period and once during the meal that they skip during the fast period. Each week, participants and their support partner will also receive a text message noting how many days in the previous week they successfully fasted for at least 16 hours. After the 12 week intervention, these text messages will stop, but for the entire 18-week period, participants in this arm will receive the same text messages as the attention control arm: A daily text message asking if they fasted for at least 16 hours over the previous 24 hours, and a weekly text message asking for weight and blood pressure results.

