#### 5.2. Sample Size

With 34 patients (17 per arm), we will have 90% power to detect a 1 day per week difference in adherence to IF, assuming a standard deviation in days fasted per week < 1.24 The study will

have  $\sim 50\%$  power to detect a 10 mmHg change in systolic and diastolic blood pressure (assuming a standard deviation of 15 mmHg) and a 3 kg weight loss (assuming a standard deviation of 5 kg).

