#### 6.6 Risk/benefit

## 6.6.1 Potential study risks

Both arms will be instructed to pursue an IF dietary pattern, which has been shown to be generally safe across multiple studies. Potential adverse effects of IF include irritability, hunger, difficulty with concentration, development of an eating disorder, disrupted sleep, dehydration and dizziness, and feelings of guilt and increased stress. There is a theoretical risk of hypoglycemia and pancreatitis. At the start of the study, patients will be given information on risks of IF and guidance on when to seek medical attention. They will also be encouraged to consume plenty of fluids during their daily fasting period. Patients on insulin or insulin secretagogues will be excluded from participation, limiting the risk of iatrogenic hypoglycemia, but patients with diabetes mellitus will be asked about episodes of hypoglycemia via weekly text messages, and all patients will be asked about hospitalizations and emergency room visits via weekly text messages.

Another potential risk of this study is a breach of participant confidentiality. We will minimize this risk by using secure data methods as described previously. Names and addresses will be stored in encrypted databases. These data will be viewable only by the respective participants, the study coordinator(s) and the project manager(s). All other members of the research team will be able to view only participant ID numbers. Even the study arms will be identified by code letters until both the statistician and PI agree that analysis is complete.

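### A single fixed block size of 6 within strata would make about 6 of 34 assignments foreseeable to anyone who could see earlier assignments by stratum, and the plan does not say who can see them

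*Combined protocol and SAP*

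**What the plan says.** Section 3.1 gives the size: "The study will randomize 34 patients with hypertension and obesity". Section 4.3 assigns them through the Way to Health platform to "attention control or the soft commitment device using 1:1 allocation", stratified at BMI 40 and systolic pressure 160, and "will use blocks of 6 to ensure equal allocation over time". No other block size and no random variation is mentioned. Assignment follows once home baseline readings and questionnaires are complete. Section 3.2 names one hospital's cardiology clinics and/or email as the source of patients.

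Staff contact before randomisation is described in section 4.1: interested people "will receive a reminder email and a phone call from a study coordinator for assistance with registration", and coordinators may help with the later online steps.

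Support partners are described only for the commitment arm (section 4.4.1, Soft commitment device: "There, they will identify a support person, a family or friend who they speak to frequently and who is invested in their health"). Section 4.1 adds: "Support partners will provide verbal informed consent via telephone for their name, email address, and phone number to be stored in the study database". Section 6.6.1 lets coordinators and project managers view stored names and addresses, and says that arms carry code letters until analysis is complete. No section describes allocation concealment, or says whether coordinators can see assignments.

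**The concern.** With one known block size, the end of a block is determined once either arm has used its three places. An assignment system can be safe against tampering and still be foreseeable.

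There is a plausible leak. A patient with a partner on record is a commitment-arm patient, whatever letter the arm carries. If the people who take partner consent, or who can see stored partner details, also help others to finish registration and surveys, they could build a tally and could influence who completes the baseline steps, and when.

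The stake is the primary outcome, self-reported days fasted per week, compared by a t test without blinding of participants (sections 5.1 and 5.3). Likely persistence may show during enrolment help. Selecting on it would make the arms differ at entry in the trait being measured, and the t test can neither detect nor correct that.

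**Working it through.** **Inputs.** N = 34 (section 3.1); 1:1, blocks of 6, four strata (section 4.3). Blocks are taken to run separately within each stratum, as section 4.3 implies. The documents give no stratum proportions, so splits are assumed and a range is shown. The plan states no predictability figure, so there is none to reproduce.

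**Step 1: one complete block.** There are 20 equally likely 3:3 sequences. An assignment is certain when one arm has already used its 3 places.
- Positions 1 to 3: never certain.
- Position 4: first three alike, 2/20 = 0.1.
- Position 5: first four split 3:1, 8/20 = 0.4.
- Position 6: always, 1.0.

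Sum: 0.1 + 0.4 + 1.0 = 1.5 of 6, or 25%. Always guessing the arm with more places left is right with probability 0.5, 0.6, 0.6, 0.7, 0.7, 1.0 by position: 4.1 of 6, or 68%.

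**Step 2: 34 patients in four strata.** Each complete block adds 1.5. A part block adds 0 for up to 3 patients, 0.1 for 4 and 0.5 for 5.

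| Split | Certain assignments |
|---|---|
| 9/9/8/8 | 1.5 + 1.5 + 1.5 + 1.5 = 6.0 |
| 14/8/8/4 | 3.0 + 1.5 + 1.5 + 0.1 = 6.1 |
| 19/8/5/2 | 4.5 + 1.5 + 0.5 + 0 = 6.5 |
| 22/4/4/4 (lowest) | 4.6 + 0.1 + 0.1 + 0.1 = 4.9 |
| 34/0/0/0 (highest) | 7.5 + 0.1 = 7.6 |

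So about 6 of 34 (6/34 = 18%) are certain to a fully informed observer. The best guess is right about 22 times of 34 (65%), against 17 by chance.

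**Step 3: varying block sizes.** Simulation with sizes drawn at random from 4, 6 and 8, and an observer who knows that set and the full history in the stratum, gives 1.7% to 2.8% certain over the assumed splits: 0.017 × 34 = 0.6 to 0.028 × 34 = 0.95. Best-guess accuracy stays at about 65%. Including size 2 is unhelpful: with 2, 4 and 6, some 40 to 42% of assignments can be predicted with at least 80% probability, against 18 to 19% with fixed 6.

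**Step 4: illustration of bias.** Assume that staff shift the entrant's expected adherence by 0.5 day/week towards the foreseen arm, with SD 1 day/week. If they act only on certainty, the false difference is about 0.5 × (certain assignments)/17. With fixed 6 this is 0.5 × 6.0/17 = 0.18 to 0.5 × 6.5/17 = 0.19 day/week. With 4/6/8 it is about 0.5 × 0.6/17 = 0.02 to 0.5 × 0.95/17 = 0.03. Simulated two-sided 5% tests then reject about 7 to 8% of the time with fixed 6, and about 5 to 6% with 4/6/8.

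The advantage depends on how sure staff must be before they act:

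| Staff act when | Fixed 6 | Random 4/6/8 |
|---|---|---|
| certain | 0.18–0.19 | 0.02–0.03 |
| at least 80% sure | 0.18–0.19 | 0.11–0.12 |
| at least 75% sure | 0.21–0.23 | 0.22–0.25 |
| any best guess | 0.30–0.32 | 0.31–0.32 |

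(False difference in days/week.) In the last two rows the schemes are alike, with type I error about 8 to 10% and 11 to 13%.

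**The case against.** The strongest objection is that the fully informed observer is not in the documents, and most of it stands.

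- **Tally.** No section says who takes partner consent, or that coordinators can see assignments. Partner contact marks only the commitment arm; a control is inferred from its absence. A commitment patient who has not yet named anyone looks the same, so any tally would be late and ambiguous.
- **Stratum.** The entrant's stratum may depend on home readings that reach the platform just before assignment. Screening values would give staff an idea of it, not certainty; the text does not say which values are used.
- **Opportunity.** Equipment is mailed, the baseline prompt is automated and the platform assigns. No section describes staff chasing baseline readings.
- **Remedy.** Varying block sizes do not help against someone who acts on a 75% or weaker guess, as the table shows.

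Two counter-arguments carry less weight. Code letters do not hide which patients have a partner, and section 6.6.1 does not say that coordinators are masked. Platform assignment prevents altering an allocation, not foreseeing it.

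A reader might infer that enrolling staff will know six assignments beforehand, or that the primary result will be biased. The documents support neither. They show a predictable scheme and a possible leak, not a tally, staff knowledge of the block size during enrolment, or any intention to steer.

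**Conclusion.** The point holds as a gap in allocation concealment. One fixed block size within four strata, with no stated limit on who sees past assignments, would make about 6 of 34 assignments (4.9 to 7.6) certain to a fully informed observer. That is an upper case, resting on a complete tally by stratum, knowledge of the entrant's stratum and separate blocks per stratum.

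The bias and type I error figures for acting on certainty alone are illustrations under assumed steering at every such slot, with assumed shift and SD. If nobody steers, there is no bias under either scheme. The sample size statement in section 5.2 is not in question here. The point ranks as a cheap improvement.

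**What to change.** In section 4.3, replace "will use blocks of 6 to ensure equal allocation over time" with wording to this effect:

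*will use permuted blocks of randomly varying size within strata, generated in Way to Health; block sizes, the sequence, and past assignments by stratum are not visible to staff who assist participants before randomisation.*

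Keep the actual sizes (for example 4, 6 and 8, without 2) in a restricted randomisation file and out of the protocol. State who takes partner consent and who can view partner details, and where possible separate those people from the staff who assist enrolment. Restricting the view of past assignments is the more important part, because it also limits best-guess steering; varying the sizes removes only certain knowledge.

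Cost: a short protocol change and, presumably, a platform setting and access rights; no extra patients or visits. Separating the roles may take some arranging in a small team. An unfinished block of 8 can leave a stratum out of balance by up to 4, against 3 with blocks of 6.
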